# 5.2 Endpoints

# 5.2.1 Primary Safety Endpoint

The frequency and severity of all unanticipated adverse device-related events (UADE) or treatment-related adverse events, during and after implantation of the CorNeat KPro device up to 12 months should be less than SOC (as detailed in section Known Potential Risks).

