# Study endpoints:

# Primary Safety Endpoint:

The frequency and severity of all unanticipated adverse device-related events (UADE) or treatment-related adverse events, during and after implantation of the CorNeat KPro and up to 12 months should be less than SOC (as detailed in section Known Potential Risks).

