# 4.2.4 Indications for Use

The ultimate intent of CorNeat Vision is to approve the CorNeat KPro as an **alternative to SOC - penetrating, or full thickness, corneal transplantation (Penetrating Keratoplasty, PKP)** where patient tissue is replaced with donor tissue. Section 4.2.6 below outlines PKP indications. Given the commercial and clinical risks involved, CorNeat Vision plans to undertake a stepwise approach, initially seeking approval of the CorNeat KPro device and implantation kit for patients who are poor candidates for PKP. For these indications there is a regulatory precedent as documented in FDA guidance on 510(k) submissions for KPros dated March 3, 1999. These initial indications for use are similar to those that apply to commercially available synthetic corneal implants, such as the Boston KPro. Section 4.2.54.2.5 outlines current indications of use for KPros. The initial intended use for the CorNeat KPro is defined below and is consistent with the FDA's definition of Class II special controls.

Per the FDA guidance for the initial first step, The CorNeat KPro device will be defined as a "keratoprosthesis device implanted permanently to provide a transparent optical pathway through an opacified cornea in an eye that is not a reasonable candidate for a corneal transplant."

As a second step, and once the device safety is validated in a limited clinical study (per the applicable FDA guidance), CorNeat Vision plans to take the necessary steps and initiate additional clinical trial/s and expand the indications for use to also cover those of PKP. In the treatment of corneal opacities, keratoplasty is the SOC. For some medical indications causing corneal opacities, failure rates of keratoplasty are unacceptable. Patients not suitable

**CONFIDENTIAL** - THIS DOCUMENT CONTAINS CONFIDENTIAL AND PROPRIETARY INFORMATION. THIS DOCUMENT MAY NOT BE REPRODUCED, USED, OR DISCLOSED TO ANY THIRD PARTY WITHOUT PRIOR WRITTEN CONSENT.

for keratoplasty may attempt keratoprosthesis implantation as a last resort. The following sections outline the major indications for both patient groups.

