#### 7.2.2 Exclusion Criteria

- 7.2.2.1 Reasonable chance of success with traditional keratoplasty
- 7.2.2.2 Current retinal detachment
- 7.2.2.3 Connective tissue diseases
- 7.2.2.4 End stage glaucoma
- 7.2.2.5 History or evidence of severe inflammatory eye diseases (i.e. uveitis, retinitis, scleritis) in one or both eyes within 6 months prior to planned implantation
- 7.2.2.6 History of ocular or periocular malignancy
- 7.2.2.7 History of extensive keloid formation
- 7.2.2.8 Any known intolerance or hypersensitivity to topical anaesthetics, mydriatics, or component of the device
- 7.2.2.9 Signs of current infection, including fever and current treatment with antibiotics
- 7.2.2.10 Severe generalized disease that results in a life expectancy shorter than a year

UNCONTROLLED WHEN PRINTED

**CONFIDENTIAL** - THIS DOCUMENT CONTAINS CONFIDENTIAL AND PROPRIETARY INFORMATION. THIS DOCUMENT MAY NOT BE REPRODUCED, USED, OR DISCLOSED TO ANY THIRD PARTY WITHOUT PRIOR WRITTEN CONSENT.

- 7.2.2.11 Any clinical evidence that the investigator feels would place the subject at increased risk with the placement of the device
- 7.2.2.12 Corneal thickness less than 400 or higher than 1,200 microns in any region of the pachymetry map of the eye intended to be operated
- 7.2.2.13 Currently pregnant or breastfeeding
- 7.2.2.14 Participation in any study involving an investigational drug or device within the past 30 days or 5 half-lives of the drug (whichever longer) or ongoing participation in a study with an investigational drug or device
- 7.2.2.15 Intraoperative complication that would preclude implantation of the study device.
- 7.2.2.16 Vulnerable populations.

Subjects who meet all inclusion criteria and none of the exclusion criteria will be enrolled in the protocol study and implanted with the CorNeat KPro device.

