### 10.8 Known Potential Risks

Known risks from usage of similar artificial corneas are:

- Postoperative Corneal Melt is one of the most severe complications that can occur after keratoprosthesis surgery with incidence of up to 30%. It may lead to scarring, irregular astigmatism, photophobia, decreased vision, and even endophthalmitis.
- Lack of graft retention Corneal grafts tissue artificial integration is limited and with time the bond between the implant and eye weakens. E.g. Boston KPro's retention rates decreases over time with incidence of lack of retention of 6, 11 and 25% after 1, 2- and 5-years post-op, respectively.
- Post-operative Glaucoma is the most important threat to long-term preservation of vision following Boston KPro surgery with elevation of intraocular pressure in 19–38 % of patients postoperatively and progression of pre-operative glaucoma in 7–14 % of patients. Development of glaucoma de novo following Kpro placement has been reported in 2-28% of KPro recipients .
- Poor post-operative visual quality Eyes with current KPros have very limited visual field and poor visual function. About 50% of patients implanted with Boston KPro maintain 20/200 CDVA after 8 years from surgery .

<sup>6 Bouhout, S., Robert, M.C., Deli, S. and Harissi-Dagher, M., 2018. Corneal melt after Boston keratoprosthesis: Clinical presentation, management, outcomes and risk factor analysis. Ocular immunology and inflammation, 26(5), pp.693-699.

<sup>7 Schaub, F., Bachmann, B.O., Seyeddain, O., Moussa, S., Reitsamer, H.A. and Cursiefen, C., 2017. Mid-and longterm experiences with the Boston-keratoprosthesis. The Cologne and Salzburg Perspective. Klinische Monatsblatter fur Augenheilkunde, 234(6), p.770.

<sup>8 Jin, B. and Zhu, X., 2017. The pathogenesis and prevention of corneal graft melting after keratoplasty. J Clin Ophthalmol, 1(1), p.10.

<sup>9 Ciolino, J.B., Belin, M.W., Todani, A., Al-Arfaj, K., Rudnisky, C.J. and Boston Keratoprosthesis Type 1 Study Group, 2013. Retention of the Boston keratoprosthesis type 1: multicenter study results. Ophthalmology, 120(6), pp.1195-1200.

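### The primary safety endpoint must come out below standard of care, but the protocol mislabels the comparator, gives almost no usable 12-month reference rates and states no rule for the comparison

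*Protocol*

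**What the plan says.** The synopsis and section 5.2.1 set the same primary safety endpoint. The frequency and severity of unanticipated adverse device-related events (UADEs) or treatment-related adverse events "up to 12 months should be less than SOC (as detailed in section Known Potential Risks". This is more than an outcome to be described: it states a result that should be reached, and sends the reader to section 10.8 for the reference.

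On what standard of care means, section 4.2.4 is explicit: "In the treatment of corneal opacities, keratoplasty is the SOC". Section 7.2.2 excludes any subject with a "Reasonable chance of success with traditional keratoplasty".

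Section 10.8 opens with "Known risks from usage of similar artificial corneas are" and draws mainly on the Boston KPro. It gives, for example, "incidence of lack of retention of 6, 11 and 25% after 1, 2- and 5-years post-op" and "Development of glaucoma de novo following Kpro placement has been reported in 2-28% of KPro recipients".

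Section 10.2 grades adverse events as mild, moderate or severe. Section 10.5 defines a UADE as a serious effect not already identified in section 10.8 by nature, severity or degree of incidence. Section 12.2.3 plans listings, counts and percentages, and says that the study uses no statistical methods and has no separate SAP. The synopsis adds that statistical calculations are not needed.

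**The concern.** A threshold on a primary endpoint needs four things: a named comparator, a reference value for each outcome at the relevant time, a common scale, and a rule for deciding. Here the comparator's label and its source disagree, most reference values are undated or are ranges, the severity scale has no counterpart in the reference, and there is no rule.

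At stake is the study's main claim. Whether the endpoint is met would depend on choices made after the results are known: which end of a range, which follow-up time, which rule, and what to do with events that have no listed rate. A report that safety was better than standard of care would also imply a comparison with keratoplasty that was never made.

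**Working it through.** **1. Comparator.** Section 4.2.4 says standard of care is keratoplasty. Section 10.8 describes artificial corneas. Its one direct mention of penetrating keratoplasty risk, open-sky haemorrhage and vitreous prolapse, has no rate. Section 7.2.2 removes eyes likely to do well with keratoplasty. The label and the cited data therefore refer to different treatments, and the labelled treatment is one the trial population is not suited to.

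**2. Reference values in section 10.8.** Counting the retention series as one rate:

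| Outcome | Listed rate | Time point |
|---|---|---|
| Corneal melt | up to 30% | none |
| Non-retention | 6%, 11%, 25% | 1, 2, 5 years |
| Raised IOP | 19–38% | none |
| Glaucoma progression | 7–14% | none |
| De novo glaucoma | 2–28% | none |
| 20/200 vision maintained | about 50% | 8 years |
| Retro-KPro membrane | 27–47.6% | none |
| Retinal detachment | 26.7%, only after membranotomy | none |
| Endophthalmitis | 1.2–11.4% | none |

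That is nine rates: one at 12 months, one at 8 years and seven undated (five ranges, one upper limit, one conditional). By entry, the section has 7 main and 6 other risks, 13 in all. Seven of these (haemorrhage/prolapse plus the six others) carry no incidence for the event itself.

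**3. Severity.** No entry in section 10.8 is split by the section 10.2 grades, so lower severity has no reference.

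**4. UADEs.** Under section 10.5 an event qualifies in one of three ways. If it qualifies by incidence, it exceeds the section 10.8 figure by definition. If it qualifies by nature or severity, section 10.8 has no rate that applies. No UADE that occurs can be below section 10.8; only zero UADEs could count as a pass.

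**5. Rule.** The protocol states none, so the following is illustration only. *Assumed rule:* pass if x/n is below the listed rate, with n = 10.

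Non-retention, 6% at 1 year: 1/10 = 10% fails, so only 0/10 passes. P(0 events) = (1 − p)^10:

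- true rate 6%: 0.94^10 = 0.539
- true rate 12% (an arbitrary doubling): 0.88^10 = 0.279

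If dropouts are replaced (section 7.4) and n becomes 11 or 12, 1/11 = 9.1% and 1/12 = 8.3% still fail, so again only zero events pass.

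For the ranges, the largest count that passes depends on the end chosen:

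| Outcome | Lower end | Upper end | Counts whose verdict changes |
|---|---|---|---|
| Endophthalmitis, 1.2–11.4% | 0 | 1 | 1 |
| De novo glaucoma, 2–28% | 0 | 2 | 1, 2 |
| Glaucoma progression, 7–14% | 0 | 1 | 1 |
| Raised IOP, 19–38% | 1 | 3 | 2, 3 |
| Retro-KPro membrane, 27–47.6% | 2 | 4 | 3, 4 |

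**6. A formal rule would not rescue it.** With an assumed one-sided 5% exact rule, 0/10 gives an upper bound of 1 − 0.05^(1/10) = 25.9%, far above 6%. Zero events in ln 0.05 / ln 0.94 = 48.4, so at least 49 subjects, would be needed to show a rate below 6%.

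**The case against.** The strongest reply is that the endpoint's own parenthesis identifies the source, so the comparator is only mislabelled and a few words would cure that. This is fair for the label alone. It does nothing for the time points, ranges, severity or missing rule.

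Second, the count of nine depends on convention. It becomes 11 if the three retention figures are separated, or 8 if the acuity item is left out. Non-retention and acuity also correspond to the separate effectiveness endpoints in section 5.2.2. All true, but under each of these counts exactly one figure is at 12 months. Setting non-retention aside as an effectiveness outcome would leave no 12-month safety rate at all.

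Third, the pass probabilities rest on a rule the protocol never states. That stands: they illustrate the problem and are not properties of the plan.

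Fourth, the practical harm is limited. Full listings by severity and relatedness are planned, and neither the DSMB review (10.10) nor the stopping criterion (10.11) uses this wording. That also stands. The damage is confined to the conclusion on the primary safety endpoint, which is nevertheless the study's main purpose.

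Leaving the rule to a SAP is not available as a defence, because section 12.2.3 says no separate SAP is in use.

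**Conclusion.** The concern holds and should be corrected before any conclusion is drawn on the primary safety endpoint. The protocol sets a comparative threshold, points it at data for a different treatment from the one it names, and excludes any method of making the comparison. Only one of nine listed rates is at 12 months, none is severity-graded, and 7 of 13 listed risks have no incidence of their own. Under the assumed observed-proportion rule, the verdict changes with the end of the range in all five ranges. A device with twice the reference non-retention (12% against 6%) would still pass 27.9% of the time. The textual contradictions need no assumption; the probabilities assume that rule, n = 10 and independent subjects. The descriptive 10-subject design is not at fault.

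**What to change.** In the synopsis and section 5.2.1:

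- Delete the requirement to be below standard of care and its reference to section 10.8, including the severity comparison.
- State the endpoint as the number and percentage of subjects in the safety analysis set (12.2.3) with each treatment-related adverse event through 12 months, by section 10.2 grade, with exact 95% confidence intervals.
- Report UADEs separately as counts with narratives.
- If published rates are shown, call them published keratoprosthesis rates, for context only. Give each with its full range and follow-up time, or note that the time is not stated. Draw no conclusion of lower risk. Show events without a listed incidence without a comparison.

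In section 12.2.3, add the exact intervals to the planned counts and percentages. The contradiction goes once the threshold is deleted; the intervals show how little 10 subjects can exclude.

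Two alignments are worth making in the same amendment. Soften the aim of proving safety in the synopsis and section 5.1. State which section 10.3 relatedness classes count as treatment-related.

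The cost is protocol wording and a few intervals, with no extra patients, visits or data. The safety claim becomes descriptive and less favourable.

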# 5.2.2 Effectiveness Endpoints:

Primary Effectiveness Endpoint: Device retention Secondary Effectiveness Endpoint: Improvement in visual acuity

# 6 Study Design

Prospective, open label, single arm, FIH clinical study to assess Safety and efficacy of the CorNeat Keratoprosthesis for the treatment of corneal blindness Subjects will be screened by the participating clinical site's clinical team (physician and study

staff) during a screening visit. Each subject will sign the ICF (Informed Consent Form) prior to any study activities and will be evaluated for inclusion and exclusion criteria. Only eligible subjects will be enrolled in the study. Demographic data, medical history and concomitant medication use data will be collected from enrolled subjects. Subjects will be implanted with the CorNeat KPro, and followed-up for Ocular wall integrity at the implantation site (primary endpoint) and absence of conjunctival irritation at implantation site (secondary endpoint) for 12 months in 8 clinic visits. During follow up visits safety data and use of concomitant medication will be documented. Subjects successfully completing 12 months of follow-up will be monitored for device retention and other safety issues during 3 clinic visits spanning an additional 12 months (not included in the scope of this trial). Subjects accrual is planned for 12 months and overall first subject in to last subject out is planned for 24 months.

Follow up plan will include complete clinical exam, anterior segment photography and a questionnaire assessing pain and other possible subjective ramifications.

# 7 Study Population and Subject Selection

# 7.1 Study Population

10 subjects suffering from unilateral or bi-lateral corneal blindness not reasonably amenable by transplanting human tissue. The KPro can be implanted in OD or OS (selection is according to PI discretion).

UNCONTROLLED WHEN PRINTED

### 7.2 Subject Selection

#### 7.2.1 Inclusion Criteria

- 7.2.1.1 Male or female aged  $\geq$  18 and  $\leq$  80 years on the day of screening
- 7.2.1.2 Candidates must have the ability and willingness to attend all scheduled visits and comply with all study procedures
- 7.2.1.3 Keratoprosthesis surgery is indicated in cases when keratoplasty is not a reasonable option or following a verifiable history of prior failed corneal transplantation.
- 7.2.1.4 Indications that fall under poor candidate for keratoplasty include but are not limited to: herpetic keratitis, vascularized corneal scar, Ocular Cicatricial Pemphigoid, alkali burn, Steven Johnson Syndrome, and limbal stem cell deficiency;
- 7.2.1.5 Pseudophakia
- 7.2.1.6 Adequate tear film and lid function
- 7.2.1.7 Perception of light in all quadrants
- 7.2.1.8 Female patients of childbearing age must have negative pregnancy test at screening and agree to use an effective method of contraception throughout the study

#### 7.2.2 Exclusion Criteria

- 7.2.2.1 Reasonable chance of success with traditional keratoplasty
- 7.2.2.2 Current retinal detachment
- 7.2.2.3 Connective tissue diseases
- 7.2.2.4 End stage glaucoma
- 7.2.2.5 History or evidence of severe inflammatory eye diseases (i.e. uveitis, retinitis, scleritis) in one or both eyes within 6 months prior to planned implantation
- 7.2.2.6 History of ocular or periocular malignancy
- 7.2.2.7 History of extensive keloid formation
- 7.2.2.8 Any known intolerance or hypersensitivity to topical anaesthetics, mydriatics, or component of the device
- 7.2.2.9 Signs of current infection, including fever and current treatment with antibiotics
- 7.2.2.10 Severe generalized disease that results in a life expectancy shorter than a year

UNCONTROLLED WHEN PRINTED

**CONFIDENTIAL** - THIS DOCUMENT CONTAINS CONFIDENTIAL AND PROPRIETARY INFORMATION. THIS DOCUMENT MAY NOT BE REPRODUCED, USED, OR DISCLOSED TO ANY THIRD PARTY WITHOUT PRIOR WRITTEN CONSENT.

- 7.2.2.11 Any clinical evidence that the investigator feels would place the subject at increased risk with the placement of the device
- 7.2.2.12 Corneal thickness less than 400 or higher than 1,200 microns in any region of the pachymetry map of the eye intended to be operated
- 7.2.2.13 Currently pregnant or breastfeeding
- 7.2.2.14 Participation in any study involving an investigational drug or device within the past 30 days or 5 half-lives of the drug (whichever longer) or ongoing participation in a study with an investigational drug or device
- 7.2.2.15 Intraoperative complication that would preclude implantation of the study device.
- 7.2.2.16 Vulnerable populations.

Subjects who meet all inclusion criteria and none of the exclusion criteria will be enrolled in the protocol study and implanted with the CorNeat KPro device.

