#### UNCONTROLLED WHEN PRINTED

the subject at increased risk with the placement of the device; (xii) corneal thickness less than 400 or higher than 1,200 microns in any region of the pachymetry map of the eye intended to be operated; (xiii) currently pregnant or breastfeeding; (xiv) participation in any study involving an investigational drug or device within the past 30 days or 5 half-lives of the drug (whichever longer) or ongoing participation in a study with an investigational drug or device and; (xv) intraoperative complication that would preclude implantation of the study device; (xvi) Vulnerable populations

Patients who meet all inclusion criteria and none of the exclusion criteria will be enrolled in the protocol and implanted with the CorNeat Kpro device.

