# 8.1.2 Implantation

Implantation day will be recorded as day 0; enrolment day Safety data will be collected upon enrolment.

Patients will be hospitalized as decided by the surgeon, estimated 1 hospitalization day will be required. Patients will be informed that they have the right to contact the PI or designee per their discretion

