### 12.2.3 Statistical Analysis

There is not a separate Statistical Analysis Plan (SAP) document in use for the trial since no statistical methods are applied in this study.

The safety analysis set will consist of all patients who were enrolled into the study. Individual listings of adverse events including adverse events (reported term), duration, relationship to the study device, severity and the adverse events outcome will be provided for the total population, where applicable. AEs will be summarized using frequency counts and percentages.

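### An intraoperative complication is listed as an exclusion criterion while the safety set is limited to enrolled patients, so a subject operated on but left without a device can drop out of the safety counts

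*Protocol*

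**What the plan says.** Four statements in the protocol combine to decide who is counted.

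- **The exclusion.** 7.2.2.15 reads "Intraoperative complication that would preclude implantation of the study device", and the synopsis repeats it as "xv) intraoperative complication that would preclude implantation of the study device".
- **The enrolment rule.** The closing sentence of 7.2.2 reads "Subjects who meet all inclusion criteria and none of the exclusion criteria will be enrolled in the protocol study and implanted". Section 6 adds "Only eligible subjects will be enrolled in the study".
- **The safety set.** 12.2.3 states "The safety analysis set will consist of all patients who were enrolled into the study". Adverse events are then summarised as counts and percentages.
- **No other source.** The same section states "There is not a separate Statistical Analysis Plan (SAP) document in use for the trial".

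Other text bears on the same subject. 8.1.2 makes day 0 the enrolment day and adds "Safety data will be collected upon enrolment". 8.1.3 records safety parameters during surgery. 8.1.4 has a failed procedure entered in the CRF as an operative failure. Table 8.2 places the eligibility check at screening only and marks adverse events at the procedure. The primary safety endpoint in 5.2.1 covers events during implantation as well as after it.

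**The concern.** Eligibility criteria should be settled before the study intervention. This one can be met only in the course of it. Because enrolment depends on meeting no exclusion, and the safety set depends on enrolment, membership of the safety set can depend on how the study operation ended. The subjects who could be lost are exactly those with a complication serious enough to prevent implantation, and the primary endpoint is meant to cover that period.

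The case is foreseeable. 4.2.7 keeps a spare unit and a corneal graft ready in the operating room for a complication that prevents use of the dispensed unit. Two analysts could follow the protocol faithfully and report different numerators and denominators from the same data.

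**Working it through.** The plan states no figure on this point. The sample size of 10 is set on a non-statistical basis, so there is nothing to reproduce. The check is a reading of the text followed by an illustration of size.

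**Step 1: the literal chain.** A complication during surgery prevents implantation, so 7.2.2.15 is met. The subject then fails the condition in the last sentence of 7.2.2 and in section 6, and is not enrolled. Under 12.2.3 a subject not enrolled is outside the safety set.

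**Step 2: the opposite chain.** Day 0 is the enrolment day (8.1.2) and eligibility is checked at screening (Table 8.2). The subject is therefore already enrolled when the complication occurs. Intraoperative data are collected (8.1.3) and the failure goes into the CRF (8.1.4). On this chain the subject is in the safety set.

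**Step 3: does any text choose between them?**
- 8.1.4 governs recording, not analysis-set membership.
- 8.1.2 fixes a calendar day. It does not say what happens to enrolment if an exclusion is met later that day.
- 7.4 keeps dropouts in the ITT cohort but does not say that an operative failure is a dropout.
- 12.2.3 says that listings "will be provided for the total population, where applicable", but that population is not defined, and the phrase governs the listings rather than the percentages.

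No passage resolves it.

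**Step 4: size for an intraoperative event.** Take one failed attempt, with the complication as the event counted. Intervals are exact (Clopper-Pearson) 95%. For x = 0 the upper limit is 1 − 0.025^(1/n).

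| Scenario | Case kept | Case left out |
|---|---|---|
| 10 operated on (7.1 plans 10) | 1/10 = 10.0% (0.3 to 44.5%) | 0/9 = 0% (0 to 33.6%) |
| Replaced so that 10 are implanted (assumption) | 1/11 = 9.1% (0.2 to 41.3%) | 0/10 = 0% (0 to 30.8%) |

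The intervals overlap widely. What changes is whether one procedural case appears in a very small table.

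**Step 5: how often it could arise.** The protocol gives no operative failure rate. With an assumed rate p, the chance of at least one such case in 10 operations is 1 − (1 − p)^10:

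| Assumed p | Chance of at least one |
|---|---|
| 1% | 9.6% |
| 2% | 18.3% |
| 5% | 40.1% |
| 10% | 65.1% |

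**Step 6: direction for events that need a device in place.** A never-implanted subject adds to the denominator but cannot add to the numerator. With an assumed 3 corneal melts among 10 implanted subjects, 3/10 = 30.0%. Adding one never-implanted subject gives 3/11 = 27.3%. Section 10.8 quotes melt at up to 30% in keratoprosthesis recipients, so the larger denominator would favour the device on that comparison.

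**The case against.** The strongest reply is that the operating text already points to inclusion. Eligibility is checked at screening, enrolment is recorded on day 0 whatever the result of surgery, and a CRF entry for someone never enrolled would make little sense. 12.3.1 also requires the monitor to account for every subject treated. Dropping the subject requires an enrolment already recorded to be undone, and no passage provides for that. In context, 7.2.2.15 may mean no more than that the device is not implanted. This is a fair account of the likely intent, and it stands as such. It does not remove the literal rule in 7.2.2 and section 6.

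The practical effect is also small. The study is descriptive, adverse events are listed individually, and the spare unit narrows the cases to those that end with no device. That stands too.

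Three stronger readings are tempting, and the protocol does not support them:

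- **That such events would go unrecorded.** 8.1.4, 10.1 and 10.7 require them to be recorded and, where serious, unexpected or device related, reported to the sponsor.
- **That omission always flatters the device.** It does so for intraoperative events only. Step 6 shows the reverse for events that need a device in place.
- **That the DSMB would be denied data on failed attempts.** 10.10 defines its cohort as the first ten implanted subjects, but it says that the board reviews the data and states no limit to implanted subjects. The gap is inferred from silence.

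**Conclusion.** The concern holds as an unresolved conflict over membership of the safety set. Stated rules, followed literally, make that membership depend on a complication of the study procedure. Other stated rules imply the contrary, and 12.2.3 leaves no separate plan to settle the matter. The context leans towards inclusion, so a reader should not conclude that the sponsor intends to leave these subjects out.

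The effect is confined to counts and percentages, and to operations that end without a device. One such case is the difference between 1/10 and 0/9, or between 1/11 and 0/10 if the subject is replaced. Replacement, the failure rates of 1% to 10% and the three melts are all assumptions. 10.8 gives no rate for its one named intraoperative risk (suprachoroidal hemorrhage and vitreous prolapse), so the intraoperative contrast does not cross any numeric benchmark. The correction is nearly free and bears on the primary safety endpoint, so it should be made.

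**What to change.** 1. In 12.2.3, define the safety set as every subject in whom study surgery was started, implanted or not. Use it for intraoperative events and for operative failures.
2. In 12.2.3, name a separate implanted set as the denominator for post-implantation complications and retention. The rates in 10.8 with which these are compared come from keratoprosthesis recipients. A single set based on surgery started would dilute these rates.
3. Reconcile 7.2.2.15 and synopsis item (xv) with 8.1.2 and 8.1.4, so that an intraoperative complication neither reverses enrolment nor removes a subject from the safety set.
4. Optionally, state in 10.10 that the data given to the DSMB include failed attempts. This is a clarification, not the correction of a stated limit.

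The cost is wording and one additional denominator. No visits or data are added, because 8.1.3, 8.1.4 and 10.1 already provide for collection. Reported intraoperative rates may look slightly less favourable, for example 1/11 instead of 0/10.
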